### 10.4.2 Safety Endpoints

The number and percentage of subjects who had a TEAE as well as the number of TEAEs will be assessed for all TEAEs and SAEs.

Furthermore, the number and percentage of subjects who have a TEAE as well as the number of TEAEs will be assessed for all causally related TEAEs, related SAEs, AESIs, TEAEs leading to study discontinuation, related TEAEs leading to study discontinuation, TEAEs leading to IMP discontinuation, and related TEAEs leading to IMP discontinuation.

For the analysis of severity and causal relationship of AEs, the worst severity and the strongest relationship per subject and class of AE will be considered.

Laboratory safety parameters, especially the change in inflammatory markers and differential blood cell counts, will be assessed by time point and changes in routine laboratory parameters from baseline will be determined. Shifts in safety laboratory parameters outside of normal ranges compared with baseline will be investigated.

Immunogenicity will be assessed by determining the number and percentage of subjects with detection of ADAs (before and after administration of IMP).

Other safety endpoints will be exploratory, as defined in detail in the statistical analysis plan.

Non-treatment-emergent AEs will be listed.

### 10.4.3 Pharmacokinetic Endpoints

The exposure to IFX-1 in all subjects will be measured as the plasma concentration of IFX-1 determined on Day 4 and at all subsequent scheduled visits to the study site through Week 44 before administration of IMP, and at Weeks 0 (Day 4), 2, and 16 after administration of IMP using a separate infusion line. Actual PK sampling times will be determined and the plasma concentration of IFX-1 will be assessed by time point.

A PK substudy will be conducted during the Main Period, at Weeks 2 and 16, in approximately 50 of the 175 subjects participating in the Main Period (8 to 10 subjects per cohort). At these times, blood samples will be obtained for the analysis of IFX-1 in citrate plasma before IMP administration (0 h), after end of IMP administration (+ 10 min), and at 2 h ( $\pm 10$  min), 6 h ( $\pm 10$  min), 24 h ( $\pm 2$  h), and 48 h ( $\pm 2$  h) after start of IMP administration, in all cases using a separate infusion line.

The analysis of derived PK parameters will be described in a separate PK analysis plan.

### 10.4.4 Pharmacodynamic Endpoints

The PD of IFX-1 are primarily measured by plasma concentration of C5a, which is determined at prespecified times after administration of IFX-1.

Plasma concentrations of C5a and C3a and serum concentrations of CH50 will be assessed by time point and as change from Day 1.

Serum concentrations of CRP will be assessed by time point and as change from Day 1.

## 10.5 Analysis of Endpoints

### 10.5.1 Efficacy

The primary efficacy endpoint HiSCR at Week 16 will be analyzed using the MCP-Mod procedure. The MCP-Mod approach will include Hurley Stage at baseline, concomitant use of antibiotic therapy, and AN count at baseline as covariates.

---

Multiple contrast tests, which are part of the MCP-Mod procedure, will be used to test for a dose-response signal using the placebo cohort and the cohorts based on cumulative doses of 2,000 mg, 4,800 mg, 8,000 mg, and 10,800 mg as dose levels.

In the MCP-Mod procedure, dose-response models can be consistently considered as:

$$f(d, \theta) = \theta_0 + \theta_1 \cdot f^0(d, \theta^*),$$

where  $d$  denotes the respective dose, and  $f^0(d, \theta^*)$  denotes the standardized dose-response model parametrized by the vector  $\theta^*$ . In this parametrization,  $\theta_0$  denotes the location parameter,  $\theta_1$  denotes the scale parameter, and  $\theta^*$  determines the shape of the model function. For this study, a candidate set of 2 dose-response models are prespecified,  $m = 1, 2$ , which both characterize a monotonically increasing dose-response relationship:

1.  $E_{\max}$  model
2. Logistic model

For each of the standardized dose-response models  $f_m^0(d, \theta^*)$ , ( $m = 1, 2$ ) in the candidate set, the null hypothesis  $H_0^m: c_m^T \mu = 0$  will be tested against the 1-sided alternative  $H_1^m: c_m^T \mu > 0$  using a multiple contrast test with significance level  $\alpha/2 = 0.025$ , where  $c_m = (c_{m1}, \dots, c_{m5})^T$  is the optimal contrast vector representing model  $m$  and  $\mu = (\mu_1, \dots, \mu_5)^T$  denotes the HiSCR at Week 16 for the applied doses.

Single contrast tests will be used to test the null hypotheses that there is no dose-response signal for candidate model  $m = 1, 2$ . By combining the single test statistics to a multivariate test statistic and comparing this test statistic to a multivariate normal-distribution, the single tests are multiplicity adjusted and the multiple test problem is adequately considered. The maximum of the 2 test statistics will be used as a combined test statistic.

Only if a dose-response signal can be detected for at least 1 of the candidate models in terms of the multiple contrast tests, the shape of the dose-response curve and the target dose(s) of interest will be estimated.

The estimated dose-response curve will be used to estimate the MED and  $ED_{50}$ . The MED is defined as the minimum dose, at which the HiSCR at Week 16 is at least 15% higher than the HiSCR at Week 16 in the placebo group. An improvement of 15% over placebo in HiSCR at Week 16 is considered as clinically relevant [15]. The  $ED_{50}$  is defined as the minimum dose that achieves 50% of the maximum achievable effect over placebo. Standard formulas for the estimation of  $ED_{50}$  will be used and will be explicitly stated in the statistical analysis plan.

Multiple imputations will be performed for subjects with missing data on HiSCR at Week 16 who did not discontinue before Week 16 because of one of the following reasons:

- Disease relapse
- Progressive disease
- Lack of efficacy

Subjects who discontinued before Week 16 because of one of the above mentioned reasons will be treated as not having achieved HiSCR at Week 16. All further specifications for multiple imputations are based on the assumption that the number of subjects that need to have the HiSCR at Week 16 imputed, will be relatively small.

Multiple imputations will be performed based on the assumption that HiSCR response at Week 16 is missing at random, i.e. missingness will not depend on the HiSCR at Week 16 itself but will only depend on the factors in the imputation model. The factors that will be used in the multiple imputation model for HiSCR at Week 16 are HiSCR at prior visits, cohort, baseline Hurley Stage, baseline AN count, and concomitant use of antibiotics. We anticipate that baseline Hurley Stage, baseline AN count and concomitant use of antibiotics will not be

---

missing for subjects in the intent-to-treat population. The multiple imputation model will be using fully conditional specification logistic regression. We will perform 20 imputations using a random seed of 122007 using SAS PROC MI.

The MCP-Mod approach as outlined above will be applied to all 20 imputed datasets. If the MCP step results in a non-significant dose-response signal for more than one of the 20 datasets, the results will be considered as not robust enough for dose-response estimation. In this case, the Mod step will not be performed. For the estimation of the dose-response curve for each candidate model (Mod step), the individual model parameters ( $ED_{50}$  for the  $E_{max}$  model and  $ED_{50}$  and  $\delta$  for the logistic model) from the analysis on each imputed dataset will be combined using Rubin's rule.

The percentage of subjects with a response on the basis of the HiSCR (Section 8.2.2.2) determined at Week 12 before administration of IMP will be analyzed in the same way as the primary endpoint.

For all other continuous efficacy endpoints, the absolute values and changes from baseline (absolute and relative) will be summarized by display of basic descriptive statistics (e.g., number of observations (n), mean, standard deviation, minimum, median, maximum, lower quartile, upper quartile, and upper and lower boundary of the 95% CI for the mean) by time point.

Model-based analyses (e.g. analysis of covariance [ANCOVA], Poisson, and logistic regression models) for continuous, count, and binary endpoints will be defined in the statistical analysis plan as deemed necessary and possible.

All categorical efficacy endpoints will be summarized by time point using absolute and relative frequencies including 95% exact CIs based on the binomial distribution.

Sensitivity analyses will be defined for all efficacy endpoints if deemed necessary.

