## 5.6 Procedures in Case of Specific Side Effects

To date, IFX-1 has been tested in healthy subjects and subjects with early septic organ dysfunction, complex cardiac surgery, and HS. An overview of side effects (i.e., ADRs that occurred in these studies) is provided in the Investigator's Brochure.

If a side effect occurs or is suspected after administration of IMP, subjects must be closely monitored and carefully observed, and as applicable the side effect must be reported as an AE (Section 9). Any treatment deemed as medically appropriate should be initiated.

In case of the following specific types of side effects, the procedures reported below must be applied.

**Infections:** because IFX-1 blocks C5a, there is a theoretical risk of an increased rate of infections. Therefore, the investigator (and other health care professionals who take care of the subjects) should be alert to signs and symptoms of infections in general. In case a subject develops a clinical picture that is difficult to distinguish from that associated with invasive infection, routine blood cultures and early start of antibiotic treatment is recommended. In subjects with bacterial infection, depending on the severity of the infections, it is important that concomitant antibiotic therapy be administered during treatment with IFX-1 to ensure appropriate control of the source of the infection. The investigator should pay close attention to the choice of an appropriate broad spectrum antibiotic treatment according to applicable guidelines. The IMP can be temporarily or permanently interrupted at the investigator's discretion. Any invasive infection has to be reported as an adverse event of special interest (AESI) (Section 9.3).

**Meningitis/Meningococcal Sepsis:** in case of signs of meningitis at any time during the study period, the subject must be carefully observed and the guideline for "ambulatory acquired bacterial meningoenzephalitis"[22] should be followed. This includes lumbar puncture, blood culture testing, immediate start of treatment with dexamethasone and iv antibiotics (combination therapy with ampicillin and 3rd generation cephalosporin), and search for infectious focus (e.g., computed tomography or magnetic resonance tomography). The IMP should be interrupted immediately in case of signs and symptoms of meningitis and withdrawn if meningitis is confirmed.

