### 5.8.2.2 Antibiotic Therapy

Concomitant use of permitted oral antibiotic therapy for treatment of HS is permitted provided the dosing regimen (dose and frequency) has been stable during the 28 days before Screening (refer to exclusion criterion #6, Section 4.2). The dosing regimen must remain stable throughout study participation. Antibiotics taken on an “as needed” basis are not considered a stable dose.

Permitted oral concomitant antibiotics include:

- Doxycycline (at an oral dose of up to 100 mg twice daily)
- Minocycline (at an oral dose of up to 100 mg twice daily)

An adequate test of oral antibiotic therapy is considered to be at least 90 days in duration. If, after  $\geq 90$  days of oral antibiotic therapy, any of the following has occurred, the subject will be considered to have had an inadequate response, or loss of response, to oral antibiotics:

- Progression of Hurley Stage (i.e., the Hurley Stage of at least 1 affected anatomic region has progressed from II to III or, after having improved to I during the study [inclusion criterion #4, Section 4.1], progressed from I to II or from I to III)
- Subject requires at least 1 intervention (e.g., incision and drainage or intralesional injection of corticosteroid)
- Subject experiences pain interfering with activities of daily living, with unsatisfactory relief from over-the-counter analgesics (e.g., ibuprofen or acetaminophen)
- Subject experiences pain requiring opioids, including tramadol
- Subject experiences drainage interfering with activities of daily life (e.g., requires multiple dressing changes and/or change of clothes daily)
- Subject experiences an increase in the number of anatomic regions affected by HS
- Subject experiences at least 1 new abscess or 1 new draining fistula

A subject is defined as intolerant to oral antibiotic therapy when the therapy has been discontinued by a physician as a result of a significant adverse reaction to the therapy in question.

An adverse reaction is considered significant if it is at least moderately severe (i.e., the reaction causes discomfort and interrupts the subject's usual activities or functions). Examples of significant adverse reactions include, but are not limited to, the following:

- Nausea resulting in decreased oral intake
- Macular or papular eruption or erythema with pruritus or other associated symptoms
- Dizziness, disequilibrium, lightheadedness, or vertigo interfering with function

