### 5.8.2.4 Lesion Intervention

In case an acutely painful lesion occurs that requires immediate intervention, physicians may perform either of the following permitted interventions:

- Injection with intralesional triamcinolone acetonide suspension (at a concentration of up to 5 mg/mL, up to 1 mL), and incision and drainage
- If incision and drainage are performed, an over-the-counter antiseptic wash should be used. New systemic and topical therapies following incision and drainage (including antibiotics) are not permitted. Concomitant use of wound care dressings is allowed, but limited to alginates, hydrocolloids, and hydrogels

Subjects should continue using any ongoing oral and topical treatment (with the constraints described in Section 5.8.3) during the study.

The use of concomitant therapy associated with the lesion intervention(s) must be captured in the source documentation and in the eCRF.

**Main Period:** a total of 2 permitted interventions are allowed during the Main Period. An intervention can be applied to a maximum of 2 different lesions at the same visit to the study site, or to the same lesion at 2 different visits. The same lesion cannot be treated twice at the

---

same visit. If a subject requires more than 2 interventions within the first 16 weeks of the study, then they must be discontinued from the study.

**Extension Period:** a maximum of 2 interventions are permitted every 4 weeks during the Extension Period. An intervention can be applied to a maximum of 2 different lesions at the same visit to the study site, or to the same lesion at 2 different visits. Within each 4-week period, the same type of intervention cannot be applied twice on the same lesion. If a subject requires more than 2 interventions within a 4-week period, or has 2 of the same interventions for the same lesion within a 4-week period, then they must be discontinued from the study.

All the assessments and procedures scheduled for a given visit to the study site must occur before any interventions are applied. Any lesion that undergoes an intervention will be documented. The site will be required to count any lesion that undergoes an intervention as permanently present from the date of intervention, and must account for it in the source documentation and in the eCRF.

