### 5.8.3 Prohibited Therapy

The following therapies are prohibited for all subjects during the study:

- Phototherapy (UVB or psoralen and UVA)
- All biologic therapy with a potential therapeutic impact on the disease being studied including, but not limited to, the following:
  - Abatacept (Orencia®)
  - Anakinra (Kineret®)
  - Belimumab (Benlysta®)
  - Certolizumab pegol (Cimzia®)
  - Efalizumab (Raptiva®)
  - Etanercept (Enbrel®)
  - Golimumab (Simponi®)
  - Infliximab (Remicade®)
  - Natalizumab (Tysabri®)
  - Rituximab (Rituxan®)
  - Tocilizumab (Actemra®)
  - Ustekinumab (Stelara®)
- Any investigational agent
- Any other systemic medication for HS, including, but not limited to, antibiotics (except as specified in Section 5.8.2.2), methotrexate, cyclosporine, retinoids, and fumaric acid esters
- Oral or injectable corticosteroids
- Oral analgesics for HS not listed in Section 5.8.2.3
- Oral opioid analgesics for non-HS-related pain (for HS-related pain, see Section 5.8.2.3)
- New prescription topical therapies for HS
- Over-the-counter topical antiseptic washes, creams, soaps, ointments, gels, and liquids containing antibacterial agents to treat HS, not listed in Section 5.8.2
- Surgical or laser intervention for an HS lesion

---

The investigator should contact the sponsor if there are any questions regarding prior or concomitant therapy.

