## **10.7 Prior and Concomitant Therapies**

Prior and concomitant therapies will be summarized by absolute and relative frequencies by cohort and overall. Therapies will be defined as concomitant if the start or end date is later than the date of first IMP administration, or if no end date is available (ongoing therapy).

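### Does the undated antibiotic covariate let post-randomisation antibiotic use into the primary MCP-Mod test?

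*Combined protocol and SAP*

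**What the plan says.** Section 10.5.1 lists the covariates of the primary model: "The MCP-Mod approach will include Hurley Stage at baseline, concomitant use of antibiotic therapy, and AN count at baseline as covariates". The same three variables, with cohort and HiSCR at prior visits, enter the imputation model, and the section adds: "We anticipate that baseline Hurley Stage, baseline AN count and concomitant use of antibiotics will not be" missing (the sentence runs over a page break). The Week 12 HiSCR, "determined at Week 12 before administration of IMP will be analyzed in the same way as the primary endpoint", takes over the same covariates.

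The word *concomitant* appears in two other settings. In Section 5.8.2.2, "Concomitant use of permitted oral antibiotic therapy for treatment of HS is permitted", on condition that dose and frequency were stable in the 28 days before Screening and stay so during the study; the drugs are doxycycline and minocycline. In Section 10.7, which describes frequency tables of medication, "Therapies will be defined as concomitant if the start or end date is later than the date of first IMP administration", or if there is no end date.

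New antibiotics after first dose are addressed three times. After a lesion procedure, "New systemic and topical therapies following incision and drainage (including antibiotics) are not permitted". The prohibited list in Section 5.8.3 includes "Any other systemic medication for HS, including, but not limited to, antibiotics (except as specified in Section 5.8.2.2". For bacterial infections, however, Section 5.6 says "it is important that concomitant antibiotic therapy be administered during treatment with IFX-1".

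Section 10.1 leaves exact variable definitions to a statistical analysis plan, to be signed before the blind data review meeting and amendable only until unblinding. The supplied text contains no separate plan of that kind.

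**The concern.** A primary analysis should adjust only for variables fixed before treatment starts. If the antibiotic flag is built from the Section 10.7 date rule, a course begun in Week 10 counts in the same way as one running at entry. Such a flag can be affected both by the drug (Section 1.4.2 names a theoretical infection risk from C5a inhibition) and by a poor disease course. Adjusting for a common consequence of dose and response can create or hide a dose-response signal.

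The multiple contrast test is the primary test and also decides whether the dose-response curve, MED and ED50 are estimated at all. A badly defined covariate there would affect the study's main conclusion.

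**Working it through.** **1. Which reading fits the text?**

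- *Wording.* The phrase in 10.5.1 closely follows 5.8.2.2, where it denotes a stable HS regimen carried into the study. For a subject who keeps to that rule, status at Day 1 and status during treatment are the same value.
- *Company.* 10.5.1 groups the variable with two baseline variables and expects none of the three to be missing. That suits a value known at entry. A flag collected over time is cut short in anyone who leaves early.
- *Week 12.* The 10.7 rule has no upper date. Applied literally to the Week 12 model, it would count courses begun after Week 12, that is, after the outcome. That is hardly intended.
- *Entry criteria.* Section 4.2 excludes oral anti-infectives for non-HS infections in the 14 days before first dose (criterion 9c) and iv anti-infectives in the 28 days before Screening (8b). Antibiotic use at entry is therefore essentially doxycycline or minocycline for HS.
- *Citation.* 10.5.1 refers to neither 5.8.2.2 nor 10.7. The harmful reading arises only by joining 10.5.1 to a rule for summary tables.

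**2. The plan's own power figure.** Inputs from Section 10.2: response 25/30/45/55/60%; cumulative doses 0/2000/4800/8000/10,800 mg; Emax ED50 3000; logistic ED50 3500 and delta 1100; n = 29; one-sided alpha 0.025. Each contrast has non-centrality c'μ / √(c'Sc), and the larger of the two statistics is compared with a bivariate-normal critical value of about 2.08 (correlation about 0.94).

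- Probability scale, S = diag(p(1−p)/n), equal-weight contrasts: non-centralities 3.359 and 3.486, power 93.3%. With variance-optimal contrasts it is 93.0%.
- Logit scale, S = diag(1/(n p(1−p))): power 88.1% and 88.7% respectively.

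The stated figure of at least 90% is reproduced on the probability scale, and the logit results lie within 2 points of it. Section 10.2 names no covariate, so the definition of the antibiotic flag does not enter it.

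**3. When could the broad flag distort the test?** Suppose there is no dose effect. If later starts depend on dose only, the flag carries no information on response. If they depend on response only, cohort and response remain independent given the flag. Distortion needs both links together.

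**4. How large is it?** Simulation at 29 per cohort: logistic model with cohort, Hurley Stage, AN count and antibiotic flag; optimal contrasts on the adjusted logits. The documents give no rate of later starts, so all rates are assumptions. Also assumed: antibiotic use at entry 20% and not prognostic; Hurley III in 45% (log OR −0.6); AN count log OR −0.3 per SD; no missing data. Both flags were fitted to the same trials.

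Power (10,000 trials, Monte Carlo SE 0.003):

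| Later starts | Day 1 flag | Broad flag |
|---|---|---|
| 3% throughout | 0.906 | 0.906 |
| 5% on placebo to 15% at top dose | 0.906 | 0.905 |
| 5% to 25% with dose | 0.905 | 0.902 |
| 5% responders, 15% non-responders | 0.907 | 0.905 |
| 5% / 25% by response | 0.910 | 0.901 |

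One-sided type I error (20,000 trials, SE 0.001 to 0.002), with a common response of 25%, then 40%:

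| Later starts | Day 1 flag | Broad flag |
|---|---|---|
| 5% to 25%, dose only | 0.018, 0.020 | 0.019, 0.019 |
| 5% / 25%, response only | 0.019, 0.020 | 0.019, 0.020 |
| 5% / 15%, plus 10 points at top dose | 0.020, 0.022 | 0.022, 0.025 |
| 5% / 25%, plus 20 points | 0.019, 0.021 | 0.028, 0.033 |
| 5% / 40%, plus 30 points | 0.018, 0.020 | 0.053, 0.064 |

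A second, simpler simulation without Hurley Stage or AN count gave the same pattern. Across its cases with both links, type I error was 0.014 to 0.019 with the Day 1 flag and 0.014 to 0.050 with the broad flag. Its largest power loss, 0.902 to 0.872, needed starts in 40% of non-responders against 2% of responders.

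**5. What the inflating cases require.** In the top-dose cohort at 25% response there are 29 × 0.75 = 21.75 non-responders. The fourth row has 25 + 20 = 45% of them starting an antibiotic, about 9.8 subjects. The fifth has 40 + 30 = 70%, about 15.2 subjects.

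**The case for a change.** The strongest case for a change is that the document's only statistical definition of the word admits courses begun after randomisation, and that both harmful links can be traced in the text. Infections may rise with dose (Section 1.4.2), and Section 5.6 expects them to be treated. Because criterion 9c bars recent oral anti-infectives for non-HS infections, an eligible subject's oral course of that kind would have to be a post-dose start in order to count under 10.7. Prohibited HS antibiotics lead to removal only at the discretion of the investigator or sponsor (Section 6.2.2), and the full analysis set keeps everyone with one infusion, so a link with non-response is possible as well. Section 5.8 already records dates and reason for use of each medication, so a definition would cost one line.

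Part of this stands. The term is undefined in 10.5.1, and later courses can occur. The rest does not carry the point. The main route from non-response to a new antibiotic is prohibited; the route that remains, infection, is not tied to HiSCR. No passage suggests that the two links are both strong, which is what inflation needs. The simulations also have limits: they work on the logit scale, although 10.5.1 names no scale, and they leave out imputation and the rule on non-significant imputed datasets. They show order of magnitude, not the exact behaviour of the planned procedure.

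**Conclusion.** This is a missing detail of the kind that Section 10.1 assigns to the SAP, and one that an analyst would fill sensibly. Wording, grouping, entry criteria and prohibited therapies all point to stable doxycycline or minocycline use for HS at entry. Even if later courses were counted, power would change by at most 0.009 in the main simulation's cases listed above, and type I error would stay at or below 0.025 unless starts depended strongly on both dose and response. In the imputation model a post-baseline predictor is no error in itself. The 175 subjects, 29 evaluable per cohort, alpha of 0.025 and stated power of at least 90% all stay.

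The conclusion rests on two assumptions: that antibiotic starts after first dose are uncommon, or at most weakly tied to dose and response jointly; and that the SAP, which is not in the supplied text, defines the variable before unblinding as Section 10.1 requires.
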